#### Sample Size and Power Calculation

One hundred seventy-eight (178 patients will be randomized in this study, 89 per group to achieve 80% power to detect a non-inferiority margin difference between the group proportions of 0.15. The reference group (BTX-10) proportion is 0.85. The treatment group proportion (BTX-3) is assumed to be larger than 0.70 under the null hypothesis of inferiority. The power was computed for the case when the actual treatment group proportion is 0.85, that is both BTX-10 and BTX-3 had the same response rate of 0.85. The test statistic used is the one-sided Z test with a Type I error rate of 0.025.

Power	N1	N2	N	Reference (BTX-10) Responder Rate	BTX-3 Responder RatejH0	BTX-3 Responder Rate Ha
0.8	147	147	294	0.7	0.55	0.7
0.85	168	168	336	0.7	0.55	0.7
0.9	197	197	394	0.7	0.55	0.7
0.8	131	131	262	0.75	0.6	0.75
0.85	150	150	300	0.75	0.6	0.75
0.9	176	176	352	0.75	0.6	0.75
0.8	112	112	224	0.8	0.65	0.8
0.85	128	128	256	0.8	0.65	0.8
0.9	150	150	300	0.8	0.65	0.8

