At 3, 6, 9, and 12 months post-injection (± 14 days), patients will return for follow-up appointments. OAB-q SF, GRA, ICIQ-SF, patient satisfaction, 3-day voiding diary, and UA will be collected. If necessary, a UCx will be ordered for evaluation. We will also assess for adverse events and concomitant medications at each of these visits. Specific adverse events we will be tracking include urinary retention (inability to void), elevated PVR of greater than 300 cc, UTI, excessive bleeding at injection sites that requires cautery, and systemic BTX effects (systemic weakness). If at any visit the patient is found to have a UTI, they will be prompted to repeat that visits questionnaires and 3-day diary at an unscheduled visit once the prescribed UTI treatment has been completed. At the unscheduled visit AEs will be reviewed and a clinical decision will be made by an investigator if UTI symptoms are still present after treatment completion. The unscheduled visit will occur at the urology research clinic.

If a repeat botox injection is given at the 3, 6, or 9 month visit, the subject will have a 2 week follow up visit identical to visit 3 in the schedule of events before continuing to be followed every 3 months.

While in-person visits are preferable, if the patient is unwilling or unable to attend a study visit (specifically visits 4-7) they will not be withdrawn from the study. In order to assess patient safety and provide continuing follow-up, the patient may be contacted by phone and/or mail. If necessary, study information may be collected by either or both of these methods; phone (current medications, AE assessment) and/or mail (questionnaires, voiding diary). If a patient requires a remote visit, they may complete at least one, but not all visits remotely.

	Consent and Screening	Enrollment and Treatment	2 Weeks Post-BTX Visit (±7 days)	3 Months Post-BTX Visit d (± 14 days)	6 Months Post-BTX Visit d (± 14 days)	9 Months Post-BTX Visit d (± 14 days)	12 Months Post-BTX Visit (± 14 days)
	Visit 1	Visit 2	Visit 3	Visit 4	Visit 5	Visit 6	Visit 7
Consent	X						
Eligibility	X						
Demographics, Medical History	X						
OABq-SF ICIQ-SF	X		X	X	X	X	X
3-day Voiding Diary	X		X	X	X	X	X
Urinalysis, Urine Culture as needed	X	X	X	X	X	X	X
Pregnancy test before injection as needed a	X	X		X	X	X	
Post void residual (PVR) ♭			Х				
BTX injection		X					
Repeat BTX				X	X	X	

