(PVR) will be at the discretion of the provider. If the patient is a clinical non-responder by 3 months follow-up, subsequent management will be at the clinician's discretion. These patients will be followed, and data will be collected. We plan on conducting an intent to treat analysis which will identify any subject not assessed at 3 months after the first BTX injection as a treatment failure. However, patients who are clinical responders by 3 months and have return of symptoms will be eligible for retreatment. If patients undergo re-treatment, they will continue to receive the same number of injections they originally received. In other words, if they were originally randomized into the 3 injection arm, they will receive 3 injections at retreatment.

After any retreatment, patients will have a 2 Week Follow-up visit before continuing to be followed every 3 months. Findings of an elevated PVR will be addressed as stated above.

If the patient had systemic BTX effects the patient will not be offered repeat injections. If they have hematuria, UTI(s), or temporary urinary retention, they can be offered retreatment at the patient and clinician's discretion.

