#### VII. Data Analysis

**Statistical Analysis** 

#### Primary Effectiveness

The primary efficacy endpoint is defined as at least a 50% reduction in number of urgency related incontinence episodes at 3 months. The number of urgency incontinent episodes per day is measured as the average of two, 3-day, consecutive bladder diaries. Patients shall be classified as treatment successes or treatment failures based on this criterion.

The primary hypothesis is that the proportion of patients who are treatment successes with BTX-3 is non-inferior with a margin of 15% to that with BTX-10 at 3 months.

 $H_{o}: p_{BTX-3} \le p_{BTX-10} - 0.15 \text{ vs}$   $H_{a}: p_{BTX-3} > p_{BTX-10} - 0.15$ 

In the hypothesis equations, 0.15 is the clinical equivalence margin for the non-inferiority test of this hypothesis.

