#### Table Non Inferiority Sample size; Margin of 0.15 and expected delta=0

Power	N1	N2	N	Reference (BTX-10) Responder Rate	BTX-3 Responder Rate H0	BTX-3 Responder Rate Ha
0.8	89	89	178	0.85	0.7	0.85
0.85	102	102	204	0.85	0.7	0.85
0.9	120	120	240	0.85	0.7	0.85
0.8	63	63	126	0.9	0.75	0.9
0.85	72	72	144	0.9	0.75	0.9
0.9	85	85	170	0.9	0.75	0.9

Table Non Inferiority Sample size; Margin of 0.15 and expected delta=0

At 3 months, the percentage of patients who are successfully treated will be computed for each treatment group. Patients who exit the study early citing reasons of inadequate urge or incontinence reduction will be included in this analysis as *treatment failures*. Treatment-failure patients are otherwise known as *non-responders*.

The success rate in the BTX-3 group will be compared to that in the BTX-10 group using a non-inferiority at  $\alpha$  = 0.025 and  $\delta$  =.15 as shown earlier in this protocol.

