#### Data analyses

A biostatistician will perform all statistical analyses using SAS or similar statistical software. Descriptive statistics will be calculated. A completer analysis will be conducted for those who finish the study per protocol. The primary endpoint will be assessed comparing incontinence episodes per day at 3 months after BTX injection. This comparison will also be made for all other visits using t-tests or chi-square tests, as appropriate.

Secondary endpoints will include adverse events and comparisons between 3-site and 10-site groups looking at the GRA responses between 3-site and 10-site groups at 3 months (± 14 days) post injection, 3-day voiding diary and OABq-SF and ICIQ-SF at 3 months (± 14 days) post-injection. We will also compare post-injection VAS scores to assess for tolerability, satisfaction, and pain. Changes from baseline will also be analyzed. This comparison will also be made for all other visits using appropriate statistical tests.

In addition to a completer analysis, we also plan on conducting an intent to treat analyses which will identify any subject not assessed at 3 months after the first BTX injection as a treatment failure. In order to assess for all possible situations, 4 different scenarios will be run: 1) All dropouts will be considered non-responders for both groups 2) All dropouts will be considered responders for both groups, 3) Dropouts in the BTX 10 group will be considered responders and those in the BTX 3 group, non-responders, and 4) Dropouts in the BTX 10 group will be considered non-responders while those in the BTX 3 group, responders.

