#### VIII. Data Safety Monitoring Plan

Ongoing safety monitoring will be performed by the study staff, including the Principal Investigator (PI) and co-investigators. The PI will have ultimate responsibility of assuring patient safety. Safety issues will also be addressed in the annual reports to Beaumont's Investigational Review Board (IRB).

Additional data safety monitoring procedures include:

- Research Administration's Clinical Research Quality and Process Improvement Program (CRQIP) will perform in-house monitoring of the first patient enrolled after the completion of visit 1
- An audit of the study records after the first 10 patients are enrolled and at the half way point of enrollment by Urology Research Nurse that is not directly involved with the research study. This will be done to ensure the safety of patients and lack of significant adverse effects. Additional auditing may occur, as needed.
- Throughout the study all adverse effects will be reported to the research nurse and then to the PI at the time of the event. Adverse events, serious adverse events, and unanticipated problems not listed in the risks section of this protocol will be reported per IRB guidelines.

Once 25 patients have been randomized to each arm, we will assess the efficacy/futility of BTX injections based on the 3-month follow-up visit data.

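### The stated 80% power assumes complete month-3 data, the completer set as worded drops valid month-3 results, and neither planned analysis is named as deciding

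*Combined protocol and SAP*

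**What the plan says.** Sample Size and Power Calculation sets the size: "One hundred seventy-eight (178 patients will be randomized in this study, 89 per group to achieve 80% power". The inputs are a response rate of 0.85 in both arms, a margin of 0.15 and a one-sided Z test at 0.025. No loss rate or allowance for loss is given.

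The plan nevertheless provides for missing month-3 results:

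- Injection Procedure: "We plan on conducting an intent to treat analysis which will identify any subject not assessed at 3 months" as failing treatment.
- Data analyses repeats the rule: "identify any subject not assessed at 3 months after the first BTX injection as a treatment failure". It adds four scenarios for dropouts.
- The text after the second sample-size table: "Patients who exit the study early citing reasons of inadequate urge or incontinence reduction will be included in this analysis as" treatment failures.

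Data analyses also plans a second analysis: "A completer analysis will be conducted for those who finish the study per protocol". The primary endpoint is at month 3, but footnote c of the Schedule of Research Activities makes the 12-month visit the final one. The intent-to-treat analysis is introduced as an addition to the completer analysis. Neither is called primary, and nothing says what happens if they disagree.

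**The concern.** Three statements are incomplete.

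1. The number randomised equals the number the formula needs to have analysed. If a lost patient would have responded, the failure rule lowers the response rate; if lost patients are left out, the sample shrinks. Either way, power falls below the stated figure.
2. The completer set is defined by finishing the study, not by having the month-3 endpoint. A patient with a valid month-3 result who leaves at, say, month 7 counts in the intent-to-treat analysis but not among completers. In a non-inferiority trial this matters: if those who leave are mainly non-responders, both arms look better, the gap narrows, and the test leans towards non-inferiority.
3. With no deciding analysis named, the non-inferiority claim could rest on either. Intent-to-treat is not automatically the cautious choice here, because scoring equal losses as failures also shrinks a true deficit.

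**Working it through.** **Inputs from the documents.** Rate 0.85 in each arm, margin 0.15, one-sided alpha 0.025, power 80%, 89 per arm (Primary Effectiveness; Sample Size and Power Calculation). **Assumed.** Loss rates and exit rates, since the documents give none.

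**Reproducing the plan's figure.** n per arm = (1.95996 + 0.84162)² × 2(0.85)(0.15) / 0.15² = 88.95, rounded up to 89. Power = Φ(0.15/SE − 1.96), with SE = √(2 × 0.85 × 0.15/n). At n = 89, SE = 0.0535 and power is 80.02%. At n = 88 it is 79.58%. The table is correct and has no slack.

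**Power with loss d, equal in both arms and unrelated to response.**

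- Evaluable set: rate 0.85, n = 89(1 − d). At d = 10%: n = 80.1, SE = 0.0564, Φ(2.659 − 1.960) = 75.8%.
- Failure rule, with 0.85 as the rate among assessed patients: rate 0.85(1 − d), n = 89. At d = 10%: rate 0.765, SE = 0.0636, Φ(2.360 − 1.960) = 65.5%.
- Failure rule, with 0.85 already counting unassessed patients as failures: 80% at any d.

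| Assumed loss | Evaluable set (0.85 among evaluable) | Failure rule (0.85 among assessed) | Failure rule (0.85 already net of loss) |
|---|---|---|---|
| 2% | 79% | 77% | 80% |
| 5% | 78% | 72% | 80% |
| 10% | 76% | 66% | 80% |
| 15% | 73% | 61% | 80% |

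**Literal completer set.** Suppose all 89 per arm are assessed at month 3 and some leave later. Under the null the rates are 0.85 (BTX-10) and 0.70 (BTX-3). If a share a of non-responders and b of responders leave, the completer rate is p(1 − b) / [p(1 − b) + (1 − p)(1 − a)].

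- a = 20%, b = 0: 0.85/0.97 = 0.876 and 0.70/0.94 = 0.745. The 15-point deficit becomes 13.2 points.
- a = 30%, b = 0: 0.85/0.955 = 0.890 and 0.70/0.91 = 0.769. The deficit becomes 12.1 points.
- a = 30%, b = 10%: 0.765/0.87 = 0.879 and 0.63/0.84 = 0.750. The deficit becomes 12.9 points.

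Simulating these cases with binomial exit and the unpooled one-sided Z test (at least 1,000,000 trials each) gives:

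| Exit after month 3 | One-sided type I error |
|---|---|
| None | 2.6% |
| 20% of non-responders, no responders | 5.4% |
| 30% of non-responders, no responders | about 8% |
| 30% of non-responders, 10% of responders | 5.7% |
| 10% or 20% of all, unrelated to response | about 2.7% (power 76% or 71%) |

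**Type I error of the failure rule alone**, for a true 15-point deficit among assessed patients, n = 89:

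- 10% loss in both arms: 0.765 against 0.630, deficit 13.5 points, SE 0.0681, Φ(0.015/0.0681 − 1.96) = 4.1%.
- 15% loss in BTX-10 and 5% in BTX-3: 0.7225 against 0.665, deficit 5.75 points, SE 0.0690, Φ(0.0925/0.0690 − 1.96) = 27%.
- The reverse, 5% and 15%: 0.2%.

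**The case against.** Four points on the other side have weight.

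- **Loss may be small.** Methodology keeps patients who cannot attend visits 4 to 7 in the study and allows diaries by mail. Visit 4 is the month-3 visit, so a missed appointment need not be a missing endpoint. This stands, but it is not quantified and leaves the completer wording unchanged.
- **Month-3 non-responders stay under follow-up.** Injection Procedure says so. Exit of 20% or 30% of them with no responder leaving is therefore an extreme assumption, and those type I errors show direction rather than forecast.
- **The failure rule appears to lead.** It is stated in two sections, and the rule for early exits sits beside the non-inferiority test. The four scenarios read as sensitivity analyses and already contain the worst case for BTX-3. All this is fair, but no sentence ranks intent-to-treat against completers.
- **The sponsor may have meant month-3 completers.** Possibly; one sentence would settle it.

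A reader might also infer that the analysis will be picked after results by arm are known, because the Data Safety Monitoring Plan says "Once 25 patients have been randomized to each arm, we will assess the efficacy/futility of BTX injections based on the 3-month follow-up visit data" and only patients are described as blinded. The text does not support that: it does not say that arms will be compared at that look, or who would see the results. It supports only asking that the choice be made without access to results by arm.

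**Conclusion.** The point holds as a fault of statement and definition. The 80% is a no-loss figure unless 0.85 is already net of unassessed patients. The completer set as worded excludes valid month-3 endpoints. The deciding analysis is not named.

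Two stronger conclusions are tempting and not supported. The first is that 89 per arm is wrong or the trial is underpowered: the arithmetic is correct, no loss rate is given, and 66% at 10% loss requires 0.85 to be the rate among assessed patients. If 0.85 already counts unassessed patients as failures, intent-to-treat power is 80%. The second is that the completer analysis will inflate type I error. If later exit is unrelated to response, the error stays near 2.7% and only power is lost. The rise to 5.4% or about 8% needs exit concentrated in non-responders.

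All figures beyond the 88.95 and its power rest on assumed loss or exit, as labelled.

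**What to change.** 1. **Sample Size and Power Calculation.** State either that 80% assumes complete month-3 assessment or that 0.85 already counts unassessed patients as failures. Give power under the deciding rule over a stated range of loss. No extra patients are asked for.
2. **Data analyses.** Define the completer set for the primary endpoint as randomised patients with an evaluable month-3 endpoint, whether or not they stay to month 12. Say what evaluable means: Primary Effectiveness says "The number of urgency incontinent episodes per day is measured as the average of two, 3-day, consecutive bladder diaries", while Methodology lists one diary for the visit ("OAB-q SF, GRA, ICIQ-SF, patient satisfaction, 3-day voiding diary, and UA will be collected").
3. **Data analyses.** Without access to results by arm, name the deciding analysis and report the other beside it. Present the four scenarios as sensitivity analyses, with scenario 3 as the worst case for BTX-3. Note that scoring losses as failures is not automatically conservative for non-inferiority.

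Requiring both analyses to succeed is not recommended. By simulation, joint power for the failure rule plus the month-3 evaluable set is 61% at 10% equal loss, and 18% at 5% loss in BTX-10 and 15% in BTX-3. Nor does it guarantee type I error when loss is both unequal and related to response.

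**Cost.** Text changes only. The downside is a less favourable stated power if 0.85 is not already net of loss.

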#### Table Non Inferiority Sample size; Margin of 0.15 and expected delta=0

Power	N1	N2	N	Reference (BTX-10) Responder Rate	BTX-3 Responder Rate H0	BTX-3 Responder Rate Ha
0.8	89	89	178	0.85	0.7	0.85
0.85	102	102	204	0.85	0.7	0.85
0.9	120	120	240	0.85	0.7	0.85
0.8	63	63	126	0.9	0.75	0.9
0.85	72	72	144	0.9	0.75	0.9
0.9	85	85	170	0.9	0.75	0.9

Table Non Inferiority Sample size; Margin of 0.15 and expected delta=0

At 3 months, the percentage of patients who are successfully treated will be computed for each treatment group. Patients who exit the study early citing reasons of inadequate urge or incontinence reduction will be included in this analysis as *treatment failures*. Treatment-failure patients are otherwise known as *non-responders*.

The success rate in the BTX-3 group will be compared to that in the BTX-10 group using a non-inferiority at  $\alpha$  = 0.025 and  $\delta$  =.15 as shown earlier in this protocol.

#### Data analyses

A biostatistician will perform all statistical analyses using SAS or similar statistical software. Descriptive statistics will be calculated. A completer analysis will be conducted for those who finish the study per protocol. The primary endpoint will be assessed comparing incontinence episodes per day at 3 months after BTX injection. This comparison will also be made for all other visits using t-tests or chi-square tests, as appropriate.

Secondary endpoints will include adverse events and comparisons between 3-site and 10-site groups looking at the GRA responses between 3-site and 10-site groups at 3 months (± 14 days) post injection, 3-day voiding diary and OABq-SF and ICIQ-SF at 3 months (± 14 days) post-injection. We will also compare post-injection VAS scores to assess for tolerability, satisfaction, and pain. Changes from baseline will also be analyzed. This comparison will also be made for all other visits using appropriate statistical tests.

In addition to a completer analysis, we also plan on conducting an intent to treat analyses which will identify any subject not assessed at 3 months after the first BTX injection as a treatment failure. In order to assess for all possible situations, 4 different scenarios will be run: 1) All dropouts will be considered non-responders for both groups 2) All dropouts will be considered responders for both groups, 3) Dropouts in the BTX 10 group will be considered responders and those in the BTX 3 group, non-responders, and 4) Dropouts in the BTX 10 group will be considered non-responders while those in the BTX 3 group, responders.

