Consent to send out pre-screening activities may be done by telephone script with all elements of information sheet included. Participant agreement is consent to send prescreening activities. Once the participant is present for enrollment visit, a formal consent will be performed for study participation. Informed consent will be obtained from all patients prior to conducting any study activities. Consented patients will complete the OAB-g SF, ICIQ-SF, 3-day voiding diary and enrollment guestionnaire (demographics, medical history, concomitant medications, etc.) prior to study enrollment. A urinalysis (UA) will be collected at this visit as well and a urine culture (UCx) will be performed, if necessary. If the patient meets the eligibility criteria, they will be randomized (1:1) into the 3-injection site group or the 10injection site group. We plan on performing a stratified randomization so the number of BTX naïve and previous BTX responder patients will be equivalent in both arms in order to minimize selection bias. Patients will be blinded to the number of injections they will receive. Adverse events and concomitant medications will be assessed at each follow-up visit. A diary will also be completed, collected and reviewed at each follow-up visit. GRA will also be gathered at each follow up visit. Visual Analog Scores will be gathered at the end of the injection visit to assess for patient satisfaction, pain, and tolerability.

Patients will be asked to remain off any oral anticholinergic or beta-3 agonist medications, PTNS therapy, or any neuromodulation throughout the entirety of the study.

Patients will follow up two weeks post-injection (±7days) for an office visit. OAB-q SF, GRA, ICIQ-SF, 3-day voiding diary, UA and post void residual (PVR) will be collected. If necessary, a UCx will be ordered for evaluation.

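### Continuous outcomes have a baseline value, but the plan names no baseline-adjusted model and does not say whether visit values or changes from baseline govern

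*Combined protocol and SAP*

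**What the plan says.** All of this is in the combined protocol and SAP.

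- **Episodes per day** (VII, Data analyses): "The primary endpoint will be assessed comparing incontinence episodes per day at 3 months after BTX injection". The next sentence extends this to the other visits and is the only place where tests are named: "This comparison will also be made for all other visits using t-tests or chi-square tests, as appropriate". The natural reading is that the same tests apply at 3 months.
- **Secondary outcomes** (same section): between-arm comparisons cover "3-day voiding diary and OABq-SF and ICIQ-SF at 3 months (± 14 days) post-injection". No test is named for them; for the remaining visits the text says "This comparison will also be made for all other visits using appropriate statistical tests".
- **Change scores** (same section, in the paragraph on secondary endpoints): "Changes from baseline will also be analyzed". Neither a test nor a role relative to the visit-value comparison is given.
- **Baseline data** (IV. Methodology): "Consented patients will complete the OAB-g SF, ICIQ-SF, 3-day voiding diary and enrollment guestionnaire" before enrollment. The schedule of activities places the questionnaires and the diary at Visit 1.
- **Randomization** (IV. Methodology): "We plan on performing a stratified randomization so the number of BTX naïve and previous BTX responder patients will be equivalent in both arms". The stratum appears in no analysis.

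No ANCOVA, regression, mixed model or other covariate adjustment is named anywhere.

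**The concern.** A test on visit values ignores what is known about each patient before injection. A change score subtracts the whole baseline value, which is too much unless baseline and follow-up are very closely correlated. A model with baseline as covariate estimates how much to subtract.

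Two things are at stake. The first is precision. The aim is to show that 3 sites lose nothing against 10, and no margin is set for the continuous outcomes, so an unnecessarily wide interval that shows no difference could be taken as support. The second is pre-specification. If both analyses are run between arms, each outcome has two estimates, and the plan does not say which one is to be read.

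**Working it through.** **1. The plan's own figure.** The only sized analysis is the binary responder test (Sample Size and Power Calculation): rate 0.85 in both arms, margin 0.15, one-sided alpha 0.025, power 80%.

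n per arm = (1.960 + 0.842)² × (0.85×0.15 + 0.85×0.15) / 0.15² = 7.849 × 0.255 / 0.0225 = 88.95, so 89 per arm and 178 in total. This reproduces the plan, and nothing below alters it. No figure is stated for the continuous outcomes.

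**2. How far the two planned estimates can differ.** The visit-value difference minus the change-score difference equals the baseline difference between arms. With 89 per arm its chance SD is √(2/89) = 0.15 baseline SDs, so the two estimates differ by more than 0.15 SD in about a third of trials. This step needs no assumed correlation.

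**3. Relative precision.** Assumptions: equal SDs at baseline and follow-up, and a correlation r between them. The documents give no r, so a range is shown. With the visit-value comparison set to 1, the variance of the arm difference is 2(1 − r) for the change score and 1 − r² for the baseline-adjusted estimate. The gain in equivalent patients is 1/(1 − r²) − 1 over the visit value and 2(1 − r)/(1 − r²) − 1 over the change score.

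| r | Visit value | Change | Adjusted | Gain over visit value | Gain over change | 178 adjusted patients equal, by visit-value test |
|---|---|---|---|---|---|---|
| 0 | 1 | 2.00 | 1.00 | 0% | 100% | 178 |
| 0.1 | 1 | 1.80 | 0.99 | 1% | 82% | 180 |
| 0.3 | 1 | 1.40 | 0.91 | 10% | 54% | 196 |
| 0.5 | 1 | 1.00 | 0.75 | 33% | 33% | 237 |
| 0.7 | 1 | 0.60 | 0.51 | 96% | 18% | 349 |

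The adjusted interval is √(1 − r²) times as wide as the visit-value interval: 1.00, 0.995, 0.95, 0.87 and 0.71 down the table.

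**4. The same in power.** At 89 per arm and two-sided 0.05, the visit-value t-test has 80% power for a difference of (1.960 + 0.842) × √(2/89) = 0.42 SD. For that difference, the adjusted analysis has 80.0%, 80.4%, 83.6%, 89.9% and 97.5% power at the five values of r. The change score has 50.8%, 55.1%, 65.8%, 80.0% and 95.1%.

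**5. Check by simulation.** In 20,000 simulated trials of 89 per arm, the variances (visit value, change, adjusted) were 1.00, 1.43, 0.92 at r = 0.3; 1.00, 0.99, 0.75 at r = 0.5; and 0.99, 0.59, 0.50 at r = 0.7. These agree with the formulas.

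**6. Cost of adjusting.** Estimating the slope adds a variance factor of about 1 + 1/(178 − 4) = 1.006, which is a net loss only when r is near 0. The stratum term adds little, because the randomization balances it.

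**The case against.** The strongest reply is that no pre-stated decision depends on this. The sized, hypothesis-tested analysis is the binary one. It already uses baseline, since success is defined as a reduction of at least 50%, and no continuous outcome carries a margin. That stands, and it limits the weight of the point. It does not remove it, because the Objectives section names episodes per day as the primary outcome and the Data analyses section says the primary endpoint is assessed on it. The mismatch with the responder definition is a separate matter that a covariate does not settle.

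A reader might infer that every continuous outcome is to be compared by unadjusted t-tests. The text does not say so. T-tests are named only for episodes per day; for the secondary outcomes the method is left open, and that wording does not exclude ANCOVA. The defect there is an unspecified method. Likewise, the sentence on changes from baseline could mean within-arm summaries. Two competing between-arm tests are a plausible reading, not a stated plan.

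The size of the gain is also open to challenge, with reason. It is nil at r = 0 and about 1% at r = 0.1. The requirement of at least 8 voids per day narrows the baseline range and may lower r for voids, and repeat injection from month 3 may weaken the link to baseline at later visits. The change-score figures need equal SDs. That is doubtful for episodes, where 85% of patients are expected to at least halve their count, and the factors do not carry over exactly to a count model.

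**Conclusion.** The point holds as one of efficiency and pre-specification for the continuous outcomes. The plan names no baseline adjustment for outcomes that all have a baseline value, and it does not rank visit-value against change-from-baseline results.

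Under equal SDs, adjustment becomes worthwhile against the visit-value test from about r = 0.3 (10% more patients), rising to 33% at r = 0.5 and 96% at r = 0.7. Against the change score it is worth 54%, 33% and 18% at the same values. For the episode count these figures are only a guide.

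Two stronger conclusions are not supported. The plan is not biased here: under randomization both the visit-value and the change-score comparison estimate the arm difference without bias. Nor does adjustment improve every comparison for nothing: the gain depends on an r that the documents do not give, and there is a small cost. The non-inferiority conclusion and the 178 patients are unaffected.

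**What to change.** In Data analyses, replace the visit-value t-tests and any separate between-arm change-score tests by one model per outcome and visit, with 3 months as the main reading. Each model contains arm, that outcome's baseline value and the stratum (BTX-naïve or prior responder).

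- **OABq-SF, ICIQ-SF and voids per day:** ANCOVA. Report the adjusted 3-site minus 10-site difference with its 95% CI.
- **Incontinence episodes:** a negative binomial model on diary counts with an offset for diary days. Report the adjusted ratio with its 95% CI. This allows zeros, which matters because eligibility sets no minimum number of episodes. State the form in which baseline enters, since a plain log fails for a baseline of zero.
- **Missing baseline:** state a simple rule, for example filling in the mean of both arms combined.

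Mean changes within each arm can stay as description.

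The cost is one paragraph of wording and a degree of freedom or two, under about 1% of variance if r is near 0. No new data, visits or patients are needed.
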